1.3 Scientific Rationale

To better understand the innate and adaptive immune differentiation of CD8 T cells in response to a virus, we have used the YF-17D human model previously. In these studies, we:

1. Have identified a combination of surrogate markers that identifies CD8 effectors⁷ and a YFV-specific CD8 T cell epitope in HLA-A2 specific individuals and characterized it extensively⁸.
2. Plan to profile YFV-specific CD8 T cells at different stages of the response post-vaccination. We plan to identify genes that are differentially expressed in these cells and analyze how the pattern of gene expression changes as cells transit from effector and memory cell stages. The surrogate markers and the immunodominant epitope thus far identified will enable physical separation of this cell population. We also plan to profile these cells using microarray technology⁸. We plan to determine the magnitude and quality of YFV-specific T cell responses and the genetic signatures of effector CD8 T cells.

In addition, during activation of antigen specific T cells in response to YF-17D, CD8 T cells dramatically alter their expression of CD45 isoforms. However, unlike canonical CD45RO+ CD45RA- memory cells the bulk of the antigen specific CD8 T cells transition to a CCR7- CD45RA+ phenotype similar to the “TEMRA” population that accumulates in some elderly individuals. Unlike the TEMRA cells, these antigen specific cells retain proliferative capacity have the characteristics of effector memory cells. To date, little is known of the regulation of CD45 isoform expression nor its role in phenotype of effector and memory CD8 T cells. Better understanding of the role and regulation of this abundant phosphatase could allow for improved understanding of the requirement to induce effective long term CD8 memory in response to vaccine change.

3. Plan to determine the output of naïve T cells from thymus and determine the telomere length in T cells.
4. Plan to study the antibody secreting cells and memory B cell responses post-vaccination.
5. Plan to study the epigenetics, specifically, the methylation and demethylation patterns of yellow fever specific CD8 T cells as they move from naïve to effector to memory cells after vaccination. To accomplish this goal, we plan to perform leukapheresis of participants who are positive for the HLA-A202 allele.
6. Plan to study the draining axillary lymph node cells for germinal center reactivities after vaccination, in particular CD4+ T follicular cell, and their functions.
7. Assays proposed in [name] lab in La Jolla, CA:
 - Yellow fever-specific T-B cell co-culture assay in vitro to measure the B cell helper ability of the YFV-specific CD4 T cells
 - YFV-specific T cell proliferation in vitro
 - YFV specific cytokine/chemokine production in vitro
 - Phenotypical characterization of YFV-specific CD4 T cells by Flow Cytometry. This analysis also requires HLA typing of the donors.

1.4 Potential Risks and Benefits

1.4.1 Potential Risks

YF-VAX® is an FDA approved vaccine that is routinely recommended for persons 9 months of age or older who are traveling or living in a country where yellow fever is endemic. However, there are some risks associated with YF-VAX®. Mild reactions include soreness, redness, and swelling at the injection site, mild headache, muscle aches and mild fever and in up to 25% of the vaccines 5 to 10 days after vaccination. Severe reactions to the vaccine have been reported but are extremely rare. (Please refer to the Vaccine Information Sheet and Section 1.2).

1.4.2 Known Potential Benefits

Currently, CDC and WHO recommend vaccination for persons 9 months of age or older who are traveling to or living in a yellow fever endemic area¹³. YF-VAX® is highly efficacious and is protective from yellow fever virus infection, which is potentially life-threatening.

2 OBJECTIVES

2.1 Primary:

1. Isolation and characterization of yellow fever vaccine-specific adaptive immune responses: characterize the magnitude and quality of yellow fever virus-specific T cell responses, antibody secreting cells and memory B cells.
2. Determine the signatures of innate immune responses: cytokines, chemokines, dendritic cells and microarray analyses on peripheral blood mononuclear cells.

2.2 Secondary:

1. Compare the magnitude and kinetics of T and B cell responses, antibody secreting cells and memory B cells at various timepoints.
2. Isolation and characterization, and phenotypic analysis of Epstein-Barr virus, cytomegalovirus and yellow fever virus-specific CD8 T cells.

3 STUDY DESIGN

This is an observational study of immune responses to YF-17D vaccination in healthy adults. The study will be conducted at the Hope Clinic of Emory Vaccine Center.

A total of 250 healthy participants (18-45 years of age) will be enrolled into four study arms: A, B, C & D. Arm enrollment is determined by Human Leukocyte Antigen (HLA) type, current needs of the lab and/or willingness to participate in sampling procedures.

All participants will receive YF-17D on Day 0 at the FDA-approved dose and route of administration. Post-vaccination procedures are determined by arm assignment.

The study arms are as follows:

- Arm A (n = 200): HLA-A202⁺ – post-vaccination blood draws
- Arm B (n = 10): HLA-A202⁺ – post-vaccination blood draws and leukapheresis
- Arm C (n = 20): HLA-A202⁺ – post-vaccination blood draws and fine needle aspirate
- Arm D (n = 20): HLA-A202⁻ – post-vaccination blood draws

In general, follow up visits will occur on Days 3, 7, 14, 21, 28, 90, 180, and 360 post-vaccination.

Please see Study Schema in **Appendix A** for detailed flow chart of study Arms A-D.

4 STUDY ENROLLMENT

4.1 Subject Inclusion Criteria

1. Able to understand and give informed consent
2. Age 18-45 years
3. Participant agrees not to take any live vaccines 30 days before or after (14 days for inactivated, including COVID-19 vaccination) yellow fever vaccination
4. Women of childbearing potential must agree to use effective birth control throughout the duration of the study. A negative urine pregnancy test must be documented prior to vaccination. Participants who have a history of surgical sterilization or post-menopausal status >1 year, are not required to have a pregnancy test.

4.2 Subject Exclusion Criteria

1. Prior receipt of a yellow fever vaccine
2. Lived in a country/area which is endemic for yellow fever
3. Travel to country/area which is endemic for yellow fever. Subject to investigator discretion
4. History of previous yellow fever, West Nile, Dengue, St. Louis encephalitis, Japanese encephalitis vaccination or infection
5. Any history of allergy to eggs, chicken or gelatin or to any previous vaccine
6. A history of a medical condition resulting in impaired immunity (such as HIV infection, cancer, particularly leukemia, lymphoma, use of immunosuppressive or antineoplastic drugs or X-ray treatment). Persons with previous skin cancers or cured non-lymphatic tumors are not excluded from the study
7. History of HIV infection
8. Active Hepatitis B or Hepatitis C infection
9. COVID-19 infection in the last 30 days. Symptoms of COVID-19 must be completely resolved before yellow fever vaccine receipt.
10. History of any chronic medical conditions that are considered progressive (ex, diabetes, heart disease, lung disease, liver disease, kidney disease, gastrointestinal diseases and uncontrolled hypertension). Use of systemic immunosuppressive medications (ex, prednisone) for 2 weeks or more in the past 3 months
11. History of excessive alcohol consumption, drug abuse, psychiatric conditions, social conditions or occupational conditions that in the opinion of the investigator would preclude compliance with the trial
12. Thymus gland problems (such as myasthenia gravis, DiGeorge syndrome, thymoma) or removal of thymus gland or history of autoimmune disorder

13. Recipient of a blood products or immune globulin product within 42 days of the vaccination visit. Participants who received COVID mAbs for treatment are not excluded
14. Pregnant women and nursing mothers or women who are planning to become pregnant for the duration of the study
15. Any condition in the opinion of the investigator that would interfere with the proper conduct of the trial

4.3 Randomization Procedures

There is no randomization in this study. The arm to which a subject is assigned to is determined by their HLA type, current lab needs and/or willingness to participate in sampling procedures.

5 STUDY INTERVENTION

5.1 Study Product Description

YF-VAX® is manufactured by Sanofi Pasteur as one-dose vials will be purchased from the manufacturer. Vaccine will be stored at the Emory Investigational Drug service between 2 to 8°C per the manufacturer's instructions.

5.2 Dosage, Preparation and Administration of Study Product

YF-VAX® will be stored, prepared and dispensed from the Hope Clinic Investigational Drug Services (IDS) – Hope Clinic Satellite Location.

The vaccine will be administered by a nurse at the Hope Clinic with a 5/8th to ¾ inch long needle via subcutaneous injection.

5.3 Accountability Procedures for the Study Vaccine

The IDS pharmacist will maintain accurate drug accountability logs which will be kept at the IDS pharmacy until the completion of the study. Upon completion of the study, a final drug accountability will be done.

6 STUDY PROCEDURES

6.1 Screening Visit

When a potential participant presents for the screening visit, the informed consent will be reviewed, and all questions answered. Once the subject signs the informed consent, a study participant number will be assigned. Eligibility will then be determined for each participant based primarily on information gathered during the screening visit. Procedures conducted during the screening visit may include:

- Collection of medical history
- Collection of current medications
- Physical exam
- Vital signs
- Blood sample collection
- HLA typing (if not previously known)

At this visit, if the participant reports having received a vaccination against COVID-19 in the past 14 days or had a COVID-19 infection in the past 30 days, the enrollment visit will be delayed. All symptoms following a COVID-19 infection must be resolved before the enrollment visit.

6.2 Enrollment/Vaccination Visit (Day 0)

This visit will serve as an enrollment and vaccination visit for all participants. This visit may occur on the same day as the Screening Visit if the participant's HLA type is known prior to Screening. At this visit, the following activities may be performed:

- Physical exam
- Vital signs
- Collection of current medications
- Blood sample collection
- Urine pregnancy test (for women of childbearing potential)
- AE collection (any AE present prior to vaccination will be considered medical history)
- Vaccine administration
- Reactogenicity symptom diary distribution

Prior to vaccine administration, participants will be asked to read the Vaccine Information Sheet for the Yellow Fever Vaccine per CDC guidelines. After vaccination, participants will be observed for a minimum of 20 minutes for any immediate hypersensitivity reactions and will be given the International Certificate of Vaccination.

6.3 Follow-up Visits

The follow-up schedule that a participant follows will be dictated their Arm assignment and current needs of the lab (designated as optional visits). Please see Tables 1 and 2 for a full Schedule of Activities (SOA). The following activities may take place at follow-up visits.

- Review of current medications
- Blood Sample Collection
- Collection of Solicited AEs

6.4 Leukapheresis Procedure

Participants in Arm B will undergo this procedure on either Day 14 or 28. Collection of CD8 T Cells via leukapheresis will be performed in accordance with the standard practices of the Emory University Hospital Hemapheresis Center. Typically, in this procedure, approximately 12 liters of blood will be processed over about 3 to 4 hours using peripheral veins for venous access. Samples will be sent from the Hemapheresis Center to the Emory Vaccine Center Labs.

6.5 Fine Needle Aspirate Procedure

Participants in Arm C will undergo this procedure on either Day 14 or 28. Tissue sampling of an axillary lymph node will be carried out percutaneously by fine needle aspiration (FNA). This procedure will be performed in accordance with the standard practices of the Winship Cancer Center by Emory Radiology Department providers. The procedure involves tissue retrieval with a needle under sonographic guidance. Approximately 2-4 passes will be made to retrieve cytologic material. Samples will be sent from Winship to the Emory Vaccine Center Labs.

6.6 Schedule of Activities

Table 1. Schedule of Activities – Arms A (Standard), B (Leukapheresis), C (FNA) & D (HLA-A202⁻)

Visit	Screen	Day 0/ Enrollment	Day 3 ¹	Day 7 ¹	Pre- Leuka ²	Day 14	Day 21 ¹	Day 28	Day 90	Day 180	Day 360
Window (Days)	–	–	–1	± 1	–2 prior to leuka	± 1	± 5	± 5	± 28	± 30	± 90
Informed Consent	X										
Medical History	X	X ³									
Current Medications	X	X ³	X	X		X	X	X	X	X	X
Physical Exam		X									
Urine Pregnancy Test		X			X	X ³		X ³			
Vitals	X	X ³									
Confirm Eligibility	X										
Vaccination		X									
Symptom Diary		Distribute		Collect							
Leukapheresis^{2,4}						X		X			
FNA^{4, 5}						X		X			
AE Collection			X	X		X	X	X			
Blood Sample (Max Volume)⁶	20 ml	20 ml	24 ml	24 ml	5 ml	74 ml ⁷	74 ml	74 ml ⁷	106 ml	106 ml	106 ml

¹Visit may be optional based on current needs of the lab.

²Only applicable for Arm B participants.

³If needed.

⁴Only if undergoing FNA procedure that day.

⁵Participants have procedure on either Day 14 OR 28 – not both. Specific day depends on the current needs of the lab. Day 14 window: -2/+4 days; Day 28 window: ± 4 days.

⁶Only applicable for Arm C participants.

⁷Blood volume will be adjusted as per the laboratory needs at that point in time, no more than the maximum allowable.

⁸Blood sample not collected on the same day a participant undergoes leukapheresis.

7 SAFETY ASSESSMENT

7.1 Adverse Events and Serious Adverse Events

An adverse event (AE) is any untoward medical occurrence in a clinical investigation subject administered a pharmaceutical product regardless of its causal relationship to the study treatment. An AE can therefore be any unfavorable and unintended sign (including an abnormal laboratory finding), symptom or disease temporally associated with the use of a medicinal (investigational) product.

Any medical condition that is present at the time that the subject is screened will be considered as baseline and not reported as an AE. However, if the severity of any pre-existing medical condition increases, it will be recorded as an AE. The start and stop date of each reported AE will be recorded on the appropriate CRF. AEs characterized as intermittent require documentation of onset and duration of each episode.

AEs occurring during the trial-collection and reporting period will be documented appropriately regardless of relationship to study product. At each study visit, the investigator will inquire about the occurrence of AE/SAEs since the last visit. AEs will be followed through resolution.

A summary report of all AEs will be reviewed at regularly scheduled quarterly meetings by the study team.

Serious Adverse Event (SAE): An AE or suspected adverse reaction is considered “serious” if, in the view of either the Principal Investigator (PI) or appropriate sub-investigator, it results in any of the following outcomes:

- Death,
- A life-threatening AE*,
- Inpatient hospitalization or prolongation of existing hospitalization,
- A persistent or significant incapacity or substantial disruption of the ability to conduct normal life functions, or
- A congenital anomaly/birth defect.
- Important medical events that may not result in death, be life-threatening, or require hospitalizations may be considered serious when, based upon appropriate medical judgment they may jeopardize the patient or subject and may require medical or surgical intervention to prevent one of the outcomes listed in this definition. Examples of such medical events include allergic bronchospasm requiring intensive treatment in an emergency room or at home, blood dyscrasias or convulsions that do not result in inpatient hospitalization, or the development of drug dependency or drug abuse.

* Life-threatening AE. An AE is considered “life-threatening” if, in the view of either the PI, sub-investigator or sponsor, its occurrence places the patient or subject at immediate risk of death. It does not include an AE that, had it occurred in a more severe form, might have caused death.

7.2 Collection of Adverse Events

AEs and SAEs will be collected via a participant-completed reactogenicity symptom diary, participant interviews and/or direct evaluation. Participants may also reach out to study staff to report AEs. If needed, the subject may be asked to return to the Hope Clinic for additional safety procedures to further evaluate an AE or SAE.

- Solicited injection site and systemic reactogenicity AEs will be collected from the time of study vaccination through 7 days after study vaccination.
- Unsolicited non-serious AEs will be collected from the time of study vaccination through approximately 30 days after study vaccination.
- SAEs (regardless of relation to study product) will be collected for 12 months post-vaccination (or last study visit, whichever occurs first).

7.3 Assessment of Severity of Adverse Events

AEs must be assessed for severity and relationship to study product (see definitions below).

AEs will be assessed by a licensed study PI or sub-investigator using the FDA CBER Toxicity Grading Scale for Healthy Adult and Adolescent Volunteers enrolled in Preventive Vaccine Clinical Trials (Sept 2007) (see Appendix B) except:

- Unintentional weight loss is required to be reported as an AE only if it is considered to be potentially deleterious to the participant's health
- Injection Site Erythema or Redness and Injection Site Induration or Swelling will not consider interference with usual social and functional activities such that:
 - Grade 1 is: 2.5 to < 5 cm in diameter OR 6.25 to < 25 cm² surface area;
 - Grade 2 is: ≥ 5 to < 10 cm in diameter OR ≥ 25 to < 100 cm² surface area;
 - Grade 3 is: ≥ 10 cm in diameter OR ≥ 100 cm² surface area OR Ulceration OR Secondary infection OR Phlebitis OR Sterile abscess OR Drainage;
 - Grade 4 is: Potentially life-threatening consequences (e.g., abscess, exfoliative dermatitis, necrosis involving dermis or deeper tissue)

Additionally, chills and arthralgia will be graded according to the following criteria:

	Mild (Grade 1)	Moderate (Grade 2)	Severe (Grade 3)	Potentially Life Threatening (Grade 4)
Chills	Symptoms causing no or minimal interference with usual social & functional activities	Symptoms causing greater than minimal interference with usual social & functional activities	Symptoms causing inability to perform usual social & functional activities	N/A
Arthralgia	Joint pain causing no or minimal interference with usual social & functional activities	Joint pain causing greater than minimal interference with usual social & functional activities	Joint pain causing inability to perform usual and & functional activities	Disabling joint pain causing inability to perform basic self-care functions

For events not included in the protocol-defined grading system, the following guidelines will be used to quantify severity:

- **Mild (Grade 1):** Events require minimal or no treatment and do not interfere with the subject's daily activities.
- **Moderate (Grade 2):** Events result in a low level of inconvenience or concern with therapeutic measures. Moderate events may cause some interference with functioning and daily activities.
- **Severe (Grade 3):** Events interrupt the subject's daily activities and may require systemic drug therapy or other treatment. Severe events are usually incapacitating.
- **Potentially life threatening (Grade 4):** ER visit or hospitalization

7.4 Relationship to Study Intervention

The study products that must be considered in determining relationships of AEs are:

- YF-VAX®

The licensed study physician's assessment of an AE's relationship to study product is part of the documentation process, but it is not a factor in determining what is or is not reported in this trial. If there is any doubt as to whether a clinical observation is an AE, the event should be reported.

Study investigators will assess all AEs as being related or unrelated to the vaccination.

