7.4.1 Assigning AE Relationship to Study Product

An inability to exclude or "rule out" a relationship to the study product is not, in and of itself, sufficient to deem an AE "related."

Use the following definitions when reporting attribution to study product:

- Choose "Related" if there is a reasonable possibility* that the AE may be related to the study product. This choice suggests that the AE is more likely to be related than not related to the study product(s).

- Choose “Unrelated” if there is not a reasonable possibility* that the AE is related to the study agent. This choice suggests that the AE is more likely to be related to another cause rather than the study product(s).

*The U.S. Federal Drug Administration has published a final rule amending the IND safety reporting requirements under 21 CFR part 312.

- The final rule set a higher standard for reasonable possibility of relationship of study product to an adverse event.
- It defined that, for the purposes of IND safety reporting by the study sponsor, “reasonable possibility” means there is evidence to suggest a causal relationship between the study product and the adverse event.

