7.5 Reporting Adverse Events

Because YF-VAX® is an FDA-approved vaccine, AEs that meet the following criteria will be reported to the Vaccine Adverse Events Reporting System (VAERS):

- Local and Systemic Reactogenicity AEs \geq Grade 3
- Related AEs \geq Grade 3
- Related SAEs

AEs and SAEs will be reported to the Emory IRB per their guidelines.

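### The protocol provides no attribution of AEs to the research leukapheresis or lymph-node aspirate, and non-serious AE collection ends nominally 2 days after a Day 28 procedure

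*Combined protocol and SAP*

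**What the plan says.** **Procedures.** Section 3 plans 250 participants, with 10 in Arm B (leukapheresis) and 20 in Arm C (FNA of an axillary lymph node). Sections 6.4 and 6.5 put each procedure on Day 14 or Day 28. A Table 1 footnote leaves the choice of day to laboratory needs and gives windows of -2/+4 days for Day 14 and ± 4 days for Day 28.

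**Attribution.** Section 7.4 introduces its list with "The study products that must be considered in determining relationships of AEs are", and the list has one entry, YF-VAX. It then states: "Study investigators will assess all AEs as being related or unrelated to the vaccination". Section 7.4.1 defines both categories by the study product alone; Unrelated means that some other cause is more likely.

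**Recording and review.** Section 7.1 says "AEs occurring during the trial-collection and reporting period will be documented appropriately regardless of relationship to study product" and "A summary report of all AEs will be reviewed at regularly scheduled quarterly meetings by the study team", and has AEs followed to resolution. On relationship, Section 7.4 adds that "it is not a factor in determining what is or is not reported in this trial". Section 7.5 says "AEs and SAEs will be reported to the Emory IRB per their guidelines".

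**Collection periods.** Section 7.2 collects solicited AEs to Day 7, unsolicited non-serious AEs to about Day 30 and SAEs for 12 months (or to the last visit, if sooner), all counted from vaccination. Section 7.1 says "At each study visit, the investigator will inquire about the occurrence of AE/SAEs since the last visit". Section 6.3 names only solicited AEs among possible follow-up activities. The AE row of Table 1 is marked at Days 3, 7, 14, 21 and 28 and is blank at Days 90, 180 and 360.

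**The concern.** The trial adds two invasive research procedures to a licensed vaccine, yet its causality assessment and its AE periods are built around the vaccine alone. Two things follow.

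First, a harm caused by the leukapheresis or FNA and a coincidental illness receive the same code. Arm, procedure date and onset date show that an event came after a procedure, but not whether the investigator thought the procedure caused it. The only attribution available to the quarterly AE summary is to the vaccine.

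Second, because the non-serious AE period is fixed to vaccination, a procedure late in that period has little or no follow-up for new non-serious events. Two participants having the same procedure can be followed for very different times, depending on a day chosen for laboratory reasons.

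The sections that say when AEs are asked about also differ, so staff who follow different sections could collect different data after about Day 30.

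**Working it through.** The plan states no figure to reproduce here. The check is a reading of the attribution rules followed by calendar arithmetic.

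**1. Who is affected (Section 3).** (10 + 20) / 250 = 12%. Arms A and D have 200 + 20 = 220 participants and no such procedure.

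**2. Attribution.** Sections 6.4, 6.5 and 7.1 to 7.5 give no category for either procedure. Under Sections 7.4 and 7.4.1, an event judged more likely due to the procedure than to YF-VAX meets the definition of Unrelated, and so does any coincidental event.

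**3. Days of non-serious AE collection left after the procedure.** Formula: end of collection (Section 7.2) minus procedure day (Table 1 footnote).

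| Procedure | Assumed end | Permitted days | Nominal | Range |
|---|---|---|---|---|
| Day 28 | Day 30 | 24 to 32 | 30 − 28 = 2 | 30 − 24 = 6 to 30 − 32 = −2 (none) |
| Day 28 | Day 33 | 24 to 32 | 33 − 28 = 5 | 33 − 24 = 9 to 33 − 32 = 1 |
| Day 14 | Day 30 | 12 to 18 | 30 − 14 = 16 | 30 − 12 = 18 to 30 − 18 = 12 |

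Section 7.2 makes the 30 days approximate. Day 33 is the end of the Day 28 visit window (28 + 5) and is used here as a generous reading. With a Day 30 end, 5 of the 9 permitted days for a Day 28 procedure (Days 28 to 32) leave 2 days or fewer, and 2 of them (Days 31 and 32) fall after collection has ended.

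**4. Next scheduled visit.** If the Day 28 visit is the procedure day, the next visit is Day 90 ± 28, that is Days 62 to 118. The interval is nominally 90 − 28 = 62 days, with extremes of 62 − 32 = 30 and 118 − 24 = 94. Table 1 marks no AE collection at that visit.

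**5. Does the procedure window cover both procedures?** Table 1 prints eight footnotes but uses markers only up to 7. From 4 onward the markers appear to be shifted by one, so marker 4, which is on both procedure rows, fits the footnote that gives the window. If the window did not apply to leukapheresis, the Day 28 visit window of ± 5 days would give 30 − 23 = 7 days down to 30 − 33 = −3 (none), which is much the same.

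**6. Wordings side by side.** There are 8 follow-up visits (Days 3, 7, 14, 21, 28, 90, 180, 360).

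- Section 7.1 asks about AEs and SAEs at every visit; Section 7.2 stops non-serious AEs at about Day 30. Section 7.1 refers to a collection and reporting period but does not itself define it.
- Section 7.2 collects SAEs for 12 months; the Table 1 AE row is blank at 3 of the 8 visits, nominally 360 − 28 = 332 days.
- Section 6.3 names only solicited AEs; 6 of the 8 visits fall after the Day 7 limit for these.

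**The case against.** The strongest reply is that little is lost. AEs are recorded whatever their cause, relationship does not decide what is reported, all AEs are reviewed quarterly and followed to resolution, the IRB receives AEs and SAEs under its guidelines, SAEs run for 12 months, and participants may report events themselves. With 10 and 20 participants, every post-procedure event can be read individually. No procedure-harm rate is planned, and nothing forbids an investigator from noting another cause. The CRF is not among the documents and may already ask. All of this stands. It limits the point to a missing required judgement in the protocol, not missing events.

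On timing, the 2 days apply only to Day 28 procedures, whose number is unknown, and to a strict reading of an approximate limit. They restrict only new non-serious events, and the documents do not say when procedure harms would start. This also stands, but even the Day 33 reading leaves nominally 5 days and as little as 1.

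It can further be said that the timing gap and the difference between Sections 7.1 and 7.2 are alternatives: if Section 7.1 is unbounded, Day 90 catches the events; if Section 7.2 bounds it, the two do not conflict. The bounded reading is reasonable, and under it the timing gap is real. Under the other reading, Section 7.2 is contradicted. Either way the text needs a change.

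The remaining wording points are editorial. Section 6.3 lists what may happen and refers to Tables 1 and 2 for the full schedule; no Table 2 appears in the document available, and the Appendix A flow chart is not shown. The blank Table 1 cells agree broadly with the non-serious cut-off, and Section 7.2 requires SAE collection regardless.

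**Conclusion.** The point holds and should be corrected. As written, the protocol gives no attribution to the leukapheresis or FNA for the 30 participants (12%) who have one. For a Day 28 procedure it leaves nominally 2 days of non-serious AE collection, from 6 days down to none (nominally 5, from 9 down to 1, if collection runs to Day 33). Between 0 and 30 participants are exposed to the timing gap; a Day 14 procedure keeps 12 to 18 days and has little problem.

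The conclusion assumes that the CRF has no procedure-cause field, or that the protocol should state it if it does, and that the footnoted window covers both procedures. It concerns the completeness of the procedures' safety record; no planned analysis or estimate changes. The three wording differences alone would call only for editorial reconciliation.

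**What to change.** 1. **Section 7.4.** For AEs in Arms B and C, add a yes/no attribution to the leukapheresis or FNA beside the vaccine attribution, and list AEs in those arms by both. If the CRF already has this field, a sentence saying so is enough.
2. **Section 7.2.** For Arms B and C, end non-serious AE collection at the later of about Day 30 and a fixed interval after the procedure, with one contact at the end of that interval. The investigators should set its length. Collection still starts at vaccination and nobody's period is shortened.
3. **Sections 6.3, 7.1, 7.2 and Table 1.** State which AE types are asked about at each visit, including SAEs at Days 90, 180 and 360. Correct the Table 1 footnote markers at the same time.

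The cost is one CRF field for 30 participants, one contact for up to 30, and wording changes. The 220 participants in Arms A and D get no new field or contact, and no new procedure or assessor is needed.
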